Protocol Version 4.0
11May2017

Title:

Once-daily regimen with Envarsus® to optimize immunosuppression management and adherence in kidney transplant recipients

Institution:

Medical University of South Carolina

Principal Investigator:

[name]
Office: [contact]
[contact]
Email: [contact]

Sub-Investigators:

[name]
Office: [contact]
[contact]
Email: [contact]

[name]
Office: [contact]
[contact]

[name] [name]
Office: [contact]
Email: [contact]

1. Study Objectives

1. Primary objective

1. Estimate change from baseline to six months in adherence superiority measure by MMAS-8 in patients converted to a once-daily immunosuppressant regimen of Envarsus[®], everolimus, and prednisone versus patients converted to a twice-daily regimen of Envarsus[®] (once daily), MMF (twice daily), and prednisone (once daily).

2. Secondary objectives

1. Estimate the composite of treatment failure rate, defined as acute allograft rejection with a Banff grade 1A or higher, graft loss, or death at six months post-conversion, in patients converted to a once-daily immunosuppressant regimen of Envarsus[®], everolimus, and prednisone versus patients converted to a twice-daily regimen of Envarsus[®], MMF, and prednisone.

3. Outcomes 3.3.2 through 3.3.11 are considered exploratory

1. Examine subject specific change of the Memphis Medication Side Effect Scale (Appendix B2, 12) at the time of the conversion versus six months post-conversion, compared between the two arms (Appendix B2).
2. Examine subject specific change in quality of life, using the SF-36 (Appendix B3) at the time of conversion versus six months post-conversion, compared between the two arms.
3. Measure and compare time-to-event analysis of secondary objective between the two arms
 1. Patient death (time to event analysis)
 2. Biopsy proven acute rejection (Banff 1a or higher, time to event analysis)
 3. Graft loss (time to event analysis)
4. Examine the medication possession ratio (MPR) of adjunctive immunosuppressants (Everolimus or mycophenolate) during follow up between the two arms
 1. Compare the prevalence of patients with MPR >80%
5. Compare rates of adverse events and severe adverse events between the two arms
6. Perform exploratory analysis of subclinical rejection and IF/TA in patients with one year protocol biopsies as compared to three month protocol biopsies between the two arms

2. Background

1. Rationale

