 1. For the first three months (± 2 months) post-transplant, the pool of patients from which subject of this study will be recruited will receive the current standard of care. Standard of care is described as a regimen of tacrolimus IR BID (5-12ng/mL) + MMF 1g BID + prednisone QD Three months (± 2 months) post-transplant and at the time of recruitment, they are randomized to one of the two arms to either receive a complete once-a-day regimen or to receive twice-daily regimen.
 2. Post-randomization, subjects will be converted to one of the two arms, as shown below, and followed for a total period of six months (primary endpoint), or until a terminal end point is reached.
 1. Arm 1: Control-- twice-daily regimen of Envarsus QD (5 - 12ng/mL) + MMF (goal dose 1g BID) + prednisone QD for 6 months

2. Arm 2: Intervention-- once-a-day regimen of Envarsus QD (2- 5ng/mL) + everolimus QD (3-8ng/mL) + prednisone QD for 6 months
 1. Envarsus will be supplied for both Arms from Veloxis Pharmaceuticals
2. Adherence assessment
 1. Adherence to the study intervention will be assessed at all study visits noted on the Schedule of Evaluations (Section 5.1), using the eight point Morisky Medication Adherence Scale (MMAS-8) (17).
5. Clinical and laboratory evaluations
 1. Schedule of evaluations

Data Collection Schedule

Report Form		Baseline	Days Post-Conversion							
			7±2	14±3	30±5	60±7	90±7	120±7	150±7	180±7
Informed Consent Obtained		X								
Randomization		X								
Review of Inclusion and Exclusion Criteria		X								
Medical History		X								
Kidney Transplant Recipient		X								
Vital Signs		X					X			X
Review of Medications and Dosing		X								
Clinical assessment*	Adverse events, dosage and adherence, rejection, infection, hospitalization				X	X	X	X	X	X
	MMAS-8, MMSE Scale, and SF36 (15,16,20)	X								X
Laboratory Assessments	CBC and Chem-7 ¹	X*	O	O	O	O	O	O	O	X*
	Everolimus CO ₂		X*	X*	X*	X*	X	X*	X*	X*
	Tacrolimus CO ₂	X*	X*	X*	X*	X*	X	X*	X*	X*
End of Study										X

X=required; O=optional: data will be collected if performed as standard of care; *=not current standard of care

Footnotes:

1. Includes sodium, potassium, chloride, CO₂, BUN, SrCr, glucose, calcium, WBC, HgB, Hct, platelets
2. Tacrolimus and Everolimus concentrations will be 12- or 24-hour levels , drawn in the morning of each assessment

2. Timing of evaluation
 1. Pre-Randomization Evaluations
Baseline

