Evaluations listed under the baseline visit may be performed up to 14 days prior to randomization. Once the subject has been successfully screened and accepted for randomization, randomization must be completed within 48 hours.

2. Intervention and Evaluations

Once the subject has been successfully randomized, the patients will be directed to the hospital pharmacy to pick up study medications. Study evaluations must take place within the time window indicated on the Schedule of Evaluations (Section 5.1)

3. Clinical and Laboratory Assessments:

1. Laboratory evaluations will be performed at certified laboratories according to the study schedule. Required tests are specified in the Schedule of Evaluations (Section 5.1)
2. All subjects will undergo clinical assessment by the investigator or the investigator's designee in the manner and at the times specified in the Schedule of Evaluations (Section 5.1)
 1. Adverse events will be determined and defined according to Section 8 of the protocol
 2. Doses will be recorded of all immunosuppressants. The adjuvant immunosuppressant (mycophenolate or everolimus) will be counted and compared to the amount expected to be remaining based on the prescribed amount. An MPR will be calculated as follows: $(\text{Total Days' Supply in Period} / (\text{Last Fill Date} - \text{First Fill Date} + \text{Last Fill Days' Supply}))$
 3. Rejection and infection events will be recorded, as defined in Section 5.4)
 4. Hospitalization events will be determined by questioning the subject and review of hospital admissions in the EHR.
3. Graft function assessment will be monitored at regular intervals using the 4-variable abbreviated MDRD equation. It will be monitored at baseline and the end of the study for study outcomes and any time points dictated by standard of care follow-up in between those time points.

4. Definitions

1. Acute rejection is defined as a renal allograft biopsy showing grade 1A or greater, by the 1997 Banff Criteria and all updates since then. Biopsies will be performed when clinically warranted, based on changes in allograft function.
2. Rejection reversal is defined as return of serum creatinine to within 10% of baseline and/or histologic clearance by Banff Criteria
3. Resistant acute rejection is defined as no clinical or histologic improvement by renal biopsy within 7-10 days of initiation of treatment.

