4. Recurrent acute rejection is defined as rejection recurring more than two weeks after documented rejection reversal.
5. Opportunistic Infections will be defined according the American Society of Transplant Recommendations for Screening, Monitoring, and

Reporting of Infectious Complications in Immunosuppression Trials in Recipients of Organ Transplantation (Appendix C1).

5. Treatment of Acute rejection:
 1. Acute rejection will be treated per institutional protocol, listed in Appendix C2.

6. Acceptable contraception methods

Option 1 (monotherapy methods):

1. Intrauterine devices (IUDs)
2. Tubal sterilization
3. Patient's partner had a vasectomy

Option 2 (Choice one from category A AND one from category B):

1. Category A:
 - a. Estrogen and progesterone
 - i. Oral contraceptive pill
 - ii. Transdermal patch
 - iii. Vaginal ring
 - b. Progesterone only
 - i. Injection
 - ii. Implant
 - c. Barrier method
 - i. Diaphragm with spermicide
 - ii. Cervical cap with spermicide
 - iii. Contraceptive sponge
2. Category B:
 - a. Male condom
 - b. Female condom
 - c. Diaphragm with spermicide (for use with hormone therapy)
 - d. Cervical cap with spermicide (for use with hormone therapy)
 - e. Contraceptive sponge (for use with hormone therapy)

7. Intervention Discontinuation Evaluations: At the scheduled time of intervention discontinuation (EOT, last date of study), the following evaluations must be completed: vital signs, clinical assessment, CBC, CHEM-7, Everolimus CO, Tacrolimus CO. In case of subject withdrawal from study, the patient will return to standard of care medications and request to continue with final assessment using MMAS-8, MMSE Scale and SF-36 will be discussed with a qualified team member.

8. Adverse Events

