AEs and SAEs will be reported in accordance with the FDA Guidelines for Post-Marketing Reporting of Adverse Events 21 CFR 314.80 and 21 CFR 600.80

<http://www.fda.gov/medwatch/report/regs.htm>. Any serious adverse event or a non-serious adverse event that is related to the study and unexpected will be reported to the FDA, per reporting guidelines, as soon as possible, but no later than 15 working days.. Further, all serious adverse events that are related to the study and are unexpected must be reported to The Medical University of South Carolina IRB within 10 days per The Medical University of South Carolina IRB Unanticipated Problems and Adverse Events Policy and Procedures reporting guidelines.

9. Criteria for intervention discontinuation

1. The intervention will be withheld/discontinued for AE of grade 3 or higher or if requested by the study participant.
2. Additionally, the intervention will be discontinued if the subject meets criteria for the following reasons:
 1. Pregnancy: If a woman becomes pregnant or a male's female partner becomes pregnant while on-study, the subject will be required to instruct investigators immediately.
 2. Loss of graft: Defined as death or need for retransplant. Patients will be deemed a treatment failure and the intervention will be discontinued.\

10. Statistical considerations

1. Outcomes
 1. Primary outcome- Treatment efficacy, defined difference in change from baseline to six month measure by MMAS-8 in both arms.
 2. Secondary objectives
 1. Secondary outcome- Safety outcomes of treatment failure rate, defined as acute allograft rejection with a Banff grade 1A or higher, graft loss, or death at one year post-conversion in both arms.

2. Sample size estimation for the primary outcome

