Appendix B1: Morisky Medication Adherence (MMAS) Scale

MMAS-8	Points
Do you sometimes forget to take your pills?	1
People sometimes miss taking their medications for reasons other than forgetting. Thinking over the past two weeks, were there any days when you did not take your medicine?	1
Have you ever cut back or stopped taking your medicine without telling your doctor because you felt worse when you took it?	1
When you travel or leave home, do you sometimes forget to bring along your medicine	1
Did you take all your medicine yesterday?	1
When you feel like your symptoms are under control, do you sometimes stop taking your medicine?	1
Taking medicine every day is a real inconvenience for some people. Do you ever feel hassled about sticking to your treatment plan?	1
How often do you have difficulty remembering to take all of your medicine? A. Never/rarely B. Once in a while C. Sometimes D. Usually E. All the time	0-5

Adherence	MMAS-8 Score
High Adherence	0
Medium Adherence	1-2
Low Adherence	3-8

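### The MPR formula counts days on a study-ordered hold as non-adherence, which affects the exploratory MPR comparison only

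*Combined protocol and SAP*

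**What the plan says.** Section 9.1 directs that treatment be interrupted for severe events: "The intervention will be withheld/discontinued for AE of grade 3 or higher or if requested by the study participant".

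Section 5.3 covers the adjunct drug, everolimus or mycophenolate. Its remaining supply "will be counted and compared to the amount expected to be remaining based on the prescribed amount". MPR is then total days' supply divided by the sum of two terms: the days between the first and last fill dates, and the days' supply of the last fill. The formula contains no term for a hold.

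The exploratory outcomes in Section 1 compare MPR of the adjunct between arms and include a cut-off: "Compare the prevalence of patients with MPR >80"%.

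Section 8 has the adverse event form record what was done with study treatment. It asks for the start and end dates of the event, but not of any hold.

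On the questionnaire, Section 4.2 says: "Adherence to the study intervention will be assessed at all study visits noted on the Schedule of Evaluations (Section 5.1"), using MMAS-8. The MMAS-8 row of the Section 5.1 schedule is marked at baseline and day 180 only.

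**The concern.** MPR is meant to show whether a subject kept up their supply of a drug they were supposed to be taking. Under Section 9.1 the study team can order that the drug not be taken. If the subject obeys, the next refill comes later, and the formula counts the whole gap as time without drug. The instruction and the scoring rule therefore work against each other: compliance with one lowers the score under the other.

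What is at stake is the MPR comparison, above all the share of subjects above 80%. With 20 subjects per arm, each subject moved across the cut-off changes that arm's proportion by 1/20 = 5 percentage points. If holds of the adjunct are more frequent or longer in one arm, that arm looks less adherent for a reason that is really tolerability. The documents give no hold rate, so neither the size nor the direction can be predicted.

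**Working it through.** The plan gives no worked MPR, so there is no stated figure to reproduce. The check applies the Section 5.3 formula as written.

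**Inputs.** From the documents: the formula (5.3), the 80% cut-off (Section 1), six months of follow-up taken as 180 days (4.1, 5.1) and 20 subjects per arm (Section 3). Assumed: fills of 30 or 90 days, because fill length is not stated; a subject who is fully adherent apart from one hold of the adjunct; only fills before day 180 count; and a refill follows the hold.

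**Formula.** With n fills of L days and one hold of h days, every fill after the hold moves back by h. The last fill is (n − 1)L + h days after the first. So

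MPR = nL / [(n − 1)L + h + L] = nL / (nL + h).

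**Results.** The hold runs from day 60 with 30-day fills and from day 90 with 90-day fills.

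| Fill length (days) | Hold (days) | Fill days | MPR |
|---|---|---|---|
| 30 | 14 | 0, 30, 74, 104, 134, 164 | 180/194 = 92.8% |
| 30 | 28 | 0, 30, 88, 118, 148, 178 | 180/208 = 86.5% |
| 30 | 37 | 0, 30, 97, 127, 157 | 150/187 = 80.2% |
| 30 | 38 | 0, 30, 98, 128, 158 | 150/188 = 79.8% |
| 30 | 45 | 0, 30, 105, 135, 165 | 150/195 = 76.9% |
| 90 | 14 | 0, 104 | 180/194 = 92.8% |
| 90 | 28 | 0, 118 | 180/208 = 86.5% |
| 90 | 44 | 0, 134 | 180/224 = 80.4% |
| 90 | 45 | 0, 135 | 180/225 = 80.0% (not above 80%) |

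With 30-day fills the 38-day threshold is the same for a hold starting at day 30, 60, 90 or 120.

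**Shorter holds.** A shorter hold matters for a subject who already has gaps of their own. With five 30-day fills, 38 gap days in all are enough, for example 24 days of late refills plus a 14-day hold: 150/(150 + 24 + 14) = 79.8%. Without the hold days in the denominator the same record gives 150/(150 + 24) = 86.2%.

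**Effect of the fix.** Subtracting h gives nL/(nL + h − h) = 100% for every fully adherent row above. A cap is needed because a subject may refill on schedule during the hold. Six 30-day fills on time with a 28-day hold would give 180/(180 − 28) = 118.4%.

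**The case against.** The case against giving this much weight is fair on several counts. MPR is exploratory. A single hold of up to 28 days leaves a fully adherent subject at 86.5% or more, above the cut-off. Doses of all immunosuppressants are recorded, and the adverse event form notes the action on treatment, so an analyst could identify AE-driven holds afterwards. Leaving restart to clinical judgement is defensible in a 40-subject, single-center pilot. The expected pill count rests on the amount prescribed, which could be read as already excluding held doses. All of this limits the size of the problem. It does not repair the MPR formula, which is explicit and counts hold days. In an open-label trial an adjustment chosen later would be chosen with the arms known.

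A reader might infer four stronger points. The documents do not support them.

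- *The score depends on whether the action is called a hold or a stop.* It does not. The formula sees only fill dates and days' supply. What matters is whether a refill follows. A hold with no later refill scores like a permanent stop: after two 30-day fills, 60/(30 + 30) = 100%. Defining the two words in Section 9.1 would change no MPR.
- *The disagreement between Sections 4.2 and 5.1 damages the primary outcome.* Both place MMAS-8 at baseline and day 180, the only scores the primary outcome uses. They differ on interim scores, which feed no listed outcome.
- *Subjects taken off the regimen will lack a day-180 score.* The schedule marks that score as required, follow-up runs for six months or until a terminal end point, and Section 10.3 includes all subjects. The softer wording in Section 7, "request to continue with final assessment using MMAS-8, MMSE Scale and SF-36 will be discussed with a qualified team member", is for subjects who withdraw from the study. Section 10.3 names no method for missing scores, but that is general missing detail which Section 9.1 does not cause.
- *Holds will inflate MMAS-8 itself*, through "Thinking over the past two weeks, were there any days when you did not take your medicine" and "Did you take all your medicine yesterday". The first item is introduced as being about people who miss their medication. That a subject would count doses withheld on the team's order is an assumption, and only a hold within two weeks of day 180 could matter.

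**Conclusion.** The point holds for MPR. When a refill follows a study-directed hold of the adjunct, the Section 5.3 formula scores obedience to the hold as partial non-adherence. The loss is 7.2 percentage points for 14 days (100 − 92.8) and 13.5 for 28 days (100 − 86.5). The 80% line is reached at 38 days with 30-day fills or 45 days with 90-day fills, and sooner for a subject already near it. These figures rest on the assumed fill lengths, full adherence otherwise, and a refill after the hold but before day 180.

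The consequence is confined to the exploratory MPR comparison. The primary outcome is not touched, and the point supports no claim of lost power. How many subjects would be affected is unknown and may be none. The grade 3 trigger is a safety decision and is not questioned here. Which arm or arms Section 9.1 covers need not be settled for this point.

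**What to change.** In Section 5.3, add to the MPR definition: *Days on a documented study-directed hold of the adjunct are subtracted from the denominator and from the expected pill count; MPR is capped at 100%.*

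In Section 8, add hold start and restart dates to the adverse event form, beside the item on what was done with study treatment. Section 9.1 can stay as it is.

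The cost is two date fields and slightly more analysis work, with no added subjects, visits or laboratory tests. The rule should be in place before outcome data are examined.

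As a minor clean-up with no effect on the primary outcome, reword Section 4.2 to agree with the Section 5.1 schedule: MMAS-8 at baseline and day 180.

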- 1.** No formal power analysis conducted since this is a pilot study. However, the sample size proposed (n=40) would be able to observe a mean difference between groups in the change of MMAS-8 scores of 2 ± 2 points (95% CI 0.73,3.27) with 87% power. Additionally, a mean difference between groups in the change in the Memphis Side Effect Scale (MSES) of 5 ± 5 points (95% CI 1.83,8.17) would have 87% power in the current sample size. Given the average MSES score of 25 points in kidney transplant patients within 2 years of transplant, this appears to be a feasible outcome (11). In order to demonstrate noninferiority in treatment failure, it would require 400 subjects (200 in each group) to have 80% power, estimating a treatment failure rate of 20% and an acceptable difference of 10%. We expect that 70% of those approached meeting study inclusion/exclusion criteria will agree to participate and that 85% of those that consent and are enrolled in the study will complete all visits. If the 95% CIs for the actual enrollment and completion proportions are outside of these thresholds, then feasibility will not be met. If the 95% CIs encompass these expected values, then feasibility will be met.

3. Missing data and imputation methods

- 1.** Under the intention-to-treat principle, all subjects are included in the analysis. Extensive efforts will be made to keep all missing data to a minimum and minimize loss to follow-up (LTFU). However, it is likely that some missing data may occur.

11. Human subjects

1. Institutional review board (IRB) review and informed consent

- 1.** This protocol, the ICF, and any subsequent modifications must be reviewed and approved by the IRB. A signed and dated ICF must be obtained from the subject as defined in 21CFR50.3. The ICF must also be signed and dated by a member of the study staff qualified to be delegated the authority to obtain informed consent. A copy of the ICF must be given to the subject and the consent process must be documented in the subject's medical record. The PI or delegated sub-Investigator is responsible for ensuring that informed consent is obtained from each patient prior to conducting any study-related activities.

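### Section 10.2's 87% power and 95% CIs assume all 40 subjects give a six-month score; at the 34 expected to complete all visits, power is about 81%, and no primary analysis is named

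*Combined protocol and SAP*

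**What the plan says.** Section 3 (Study design) randomises 40 subjects, 20 per arm. Section 10.2 calls the trial a pilot without a formal power analysis, then states that "the sample size proposed (n=40) would be able to observe a mean difference between groups". The target it gives for the primary outcome is a "change of MMAS-8 scores of 2 ± 2 points (95% CI 0.73,3.27) with 87% power". For the MSES it adds that a difference of "5 ± 5 points (95% CI 1.83,8.17) would have 87% power in the current sample size".

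Later in the same paragraph, as a feasibility expectation, it assumes that "85% of those that consent and are enrolled in the study will complete all visits". Section 10.3 says that "Under the intention-to-treat principle, all subjects are included in the analysis" and concedes that "it is likely that some missing data may occur".

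Section 10.1 gives the primary outcome as the "defined difference in change from baseline to six month measure by MMAS-8 in both arms". No test, model, alpha or sidedness is stated anywhere. The schedule in Section 5.1 places the MMAS-8 at baseline and day 180. Section 4.2 speaks of all study visits, and the two should be reconciled. For subjects who withdraw, Section 7 says that the "request to continue with final assessment using MMAS-8, MMSE Scale and SF-36 will be discussed with a qualified team member".

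**The concern.** A change score needs a six-month MMAS-8. The only power and precision figures given are tied to the full randomised number, in a paragraph that itself expects 15% of subjects not to complete all visits. A reader therefore takes away 87% and about ±1.27 points, which is the best case.

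The unnamed analysis bears on the same estimate. The stated figures reproduce under an unadjusted comparison of change, but the plan does not commit to that or to any other analysis. The baseline score is already collected and could be used as a covariate, which in most circumstances gives a more precise comparison from the same subjects. In an open-label trial with a self-reported outcome, it is better not to leave that choice until the data have been seen.

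**Working it through.** **Inputs.** Section 3: 20 per arm. Section 10.2: difference 2 and SD 2 for MMAS-8, difference 5 and SD 5 for MSES, completion 85%. The ± value is read as a common SD of change. Two-sided 5% is inferred: it reproduces 87%, whereas one-sided 5% gives 92.8%.

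**Formulas.** With n per arm, the noncentrality is difference / (SD × √(2/n)) on 2n − 2 degrees of freedom, and power comes from the noncentral t distribution. The CI half-width is t(0.975, 2n − 2) × SD × √(2/n). Both outcomes have a standardised difference of 1 (2/2 and 5/5), so they share one power curve.

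**The plan's own figures (n = 20 per arm).** Noncentrality = 2 / (2 × √0.1) = 3.162 on 38 df, which gives power 86.9%. The MMAS-8 half-width is 2.024 × 2 × √0.1 = 1.28, so the CI is 0.72 to 3.28. The MSES half-width is 2.024 × 5 × √0.1 = 3.20, so the CI is 1.80 to 8.20. The plan's half-widths are (3.27 − 0.73)/2 = 1.27 and (8.17 − 1.83)/2 = 3.17. The differences of 0.01 and 0.03 do not matter. The stated figures are reproduced, with all 40 analysed.

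**At the expected completion.** 0.85 × 40 = 34, or 17 per arm if losses are equal. Noncentrality = 2 / (2 × √(2/17)) = 2.915 on 32 df, which gives power 80.7%. The MMAS-8 half-width is 2.037 × 2 × √(2/17) = 1.40, so the CI is 0.60 to 3.40. The MSES half-width is 3.49.

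| Evaluable (equal arms) | Power | MMAS-8 half-width | MSES half-width |
|---|---|---|---|
| 40 | 86.9% | 1.28 | 3.20 |
| 38 | 85.1% | 1.32 | 3.29 |
| 36 | 83.0% | 1.36 | 3.39 |
| 34 | 80.7% | 1.40 | 3.49 |
| 32 | 78.1% | 1.44 | 3.61 |
| 30 | 75.3% | 1.50 | 3.74 |

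Unequal losses matter little: 34 split 18/16, 19/15 or 20/14 gives 80.6%, 80.2% or 79.5%. The normal approximation gives 88.5% at 40 and 83.0% at 34, a fall of similar size.

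**Adjusting for baseline.** The documents give no correlation between baseline and six-month MMAS-8, so the following is on assumptions. With equal variances at the two times and correlation ρ, the variance of the change is 2s²(1 − ρ), and the ANCOVA residual variance is s²(1 − ρ²). The ratio is (1 + ρ)/2, which is below 1 unless ρ = 1. Simulation (bivariate normal, SD of change 2, difference 2) also allows for the estimated slope:

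| ρ (assumed) | ANCOVA, 17 per arm | ANCOVA, 20 per arm |
|---|---|---|
| 0.3 | 93.0% | 96.4% |
| 0.5 | 89.5% | 93.9% |
| 0.7 | 85.4% | 90.8% |
| 0.9 | 81.3% | 87.5% |
| unadjusted change | 80.7% | 86.9% |

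The gain is not universal. If the regression slope of the six-month score on baseline is close to 1 (six-month SD larger than baseline SD, or ρ of 0.98 with equal variances), ANCOVA power at 17 per arm is about 79% to 80%, against 80.7% unadjusted.

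**The case against.** The strongest reply is that nothing is miscalculated or hidden. The plan ties 87% openly to n = 40, disclaims a formal power analysis, and prints the 85% in the same paragraph. The drop is about 6 points and leaves power near 80%. All of that stands, and it limits the weight of the point. It does not explain why only the best-case figure is given.

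The second reply is that 34 is not the plan's analysed number. The 85% is a feasibility benchmark for completing all visits. A missed interim visit costs no primary data under the Section 5.1 schedule, and under Section 7 a withdrawn subject may still give a final MMAS-8. This also stands: 34 is derived from the all-visits rate and is not a forecast of day-180 scores. It is, however, the only completion figure the plan offers, and actual completion could also fall below it.

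The third reply is that ANCOVA is a preference resting on correlations not in the documents, and that a t-test power should not be printed as the power of an ANCOVA. The restated figure must therefore be labelled as an unadjusted t-test. Preferring ANCOVA does not need a particular correlation: the possible loss is about 1 to 2 percentage points and the likely gain is larger.

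A reader might also infer that the plan ignores the baseline score. It does not, since a change score uses baseline by subtraction. What is absent is a named analysis.

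**Conclusion.** The point holds. The 87% and both CIs describe full follow-up of all 40 subjects. At the paragraph's own completion figure, power is about 81% and the half-widths are about 1.40 (MMAS-8) and 3.49 (MSES). If at least 34 subjects give a six-month score, split about equally, power lies between about 81% and 87%. If about 32 or fewer do, it is below 80%. These figures rest on the plan's difference and SD, and on an inferred two-sided 5% t-test on change.

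Two stronger readings are not supported. A reader might infer that 87% is a wrong calculation, but it reproduces at n = 40. A reader might also infer that the trial is too small and should enrol 48 (40/0.85 = 47.1, rounded up to equal arms). The plan presents itself as a pilot, its power figure is descriptive, and no sample size change follows.

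Separately, no primary test or model is named. ANCOVA would use a score already collected and would usually raise power, though not in every case, and it would not remove bias from dropout.

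**What to change.** 1. Restate Section 10.2: about 87% power (half-width about 1.28 points) if all 40 subjects have a six-month MMAS-8, and about 81% (about 1.40) if 34 do, for an unadjusted two-sided 5% t-test on change. Do the same for MSES (half-width about 3.20 at 40, about 3.49 at 34). Leave the sample size unchanged.
2. In Section 10.1, name the primary analysis as an ANCOVA of six-month MMAS-8 on arm and baseline MMAS-8, reported as the adjusted difference with its 95% CI. Describe the t-test power in item 1 as an approximate, usually conservative guide to it, and note that ANCOVA does not remove dropout bias.

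A sentence in Section 10.3 on how a missing six-month score is handled, consistent with including all subjects, would be a useful minor addition, but this point does not rest on it.

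The cost is a less favourable printed power and a few sentences of text. There are no extra subjects, visits or questionnaires. The statistical downside of ANCOVA is a loss of about 1 to 2 percentage points of power if the regression slope is close to 1.
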